#### RESEARCH ONLY RISKS:

##### *Risk of breach in confidentiality*

Every effort will be made to protect the privacy of the research subjects. All information and data related to this study will be maintained in secured, protected space, and access will be restricted to study personnel only.

#### DATA COLLECTION

- (1) *Feasibility:* feasibility will be determined as the ability to provide adequate specimens to perform PD-L1 testing. Any specimen in which the requested assay returns as “insufficient material to perform testing” will be deemed an “inadequate” specimen. Adequacy for PD-L1 testing will be recorded.
- (2) *Radiographic Information:* Size and location of the central pulmonary lesion will be recorded. Size will be recorded as the longest axis diameter.
- (3) *Procedural Characteristics:* Procedural information to be recorded will include procedure time, amount of sedation given, and number of biopsies performed
- (4) *Diagnostic yield:* Diagnostic yield based on final cytology and/or histopathology will be determined from the results of the bronchoscopy. A biopsy that results in a specific diagnosis, either malignant or benign, that adequately explains the clinical scenario as determined by the treating physician, will be considered truly positive. Plan for further diagnostic management for patients who have a non-diagnostic procedure will be determined by the treating physician as clinical indicated.
- (5) *Complications:* Adverse event rates will be documented. Pneumothorax will be documented by post-biopsy CXR or chest ultrasonography, and the number requiring intervention, such as chest tube placement, will be recorded. Significant hemoptysis will be defined as bleeding noted at the time of procedure that requires a change in the level of care (e.g. outpatient to inpatient or inpatient to ICU) or a blood transfusion. Other adverse events that are common to bronchoscopy described above in “Risks” section will be monitored and reported by the patient or nursing staff.

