#### DATA SAFETY MONITORING PLAN

All subjects enrolled in the trial will undergo routine standard of care bronchoscopy that is indicated as medically necessary by their physicians. Prior to the bronchoscopic procedure, PI will explain the risks associated with bronchoscopy, and verify that the research only risks have been explained, and that the subject has signed an informed consent form. There are no anticipated risks, outside of the risk for the standard of care procedures for this clinical trial. All subjects are required to read, understand, and sign the informed consent form associated with the research study. Each subject will be informed of post procedure symptoms of which to be aware that may represent adverse reactions to the bronchoscopy. Symptoms that the patient will be informed to look out for include:

- Pain or difficulty with swallowing

- Difficulty breathing
- Vomiting
- Dizziness
- Abdominal or chest pain
- Continuous bright red blood in your sputum
- Fever above 100.0 degrees Fahrenheit

If the subject notes any of these symptoms, he/she is instructed to contact his/her physician, who will determine the course of action. All adverse events (AEs) will be reviewed by the medical monitor within one month of their occurrence and summarized for review. The PI will be responsible for submitting this report to the IRB at his/her institution as required. AEs and other reportable events are defined below.

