#### *Reportable Events*

##### *(1) AEs*

AEs will be defined as any untoward or unfavorable medical occurrence in a human subject, including any abnormal sign, symptom, or disease, temporally associated with the subject's participation in the research, whether or not considered related to the subject's participation in the research. Regarding AEs and SAEs, "temporally" will be defined as occurring within 24 hours post-procedure. Serious Adverse Events (SAEs) will be defined as any adverse event temporally associated with the subject's participation in research that meets any of the following criteria:

- \* results in death;
- \* is life-threatening;
- \* requires inpatient hospitalization or prolongation of existing hospitalization;
- \* results in a persistent or significant disability/incapacity;
- \* results in a congenital anomaly/birth defect; or
- \* any other adverse event that, based upon appropriate medical judgment, may jeopardize the subject's health and may require medical or surgical intervention to prevent one of the other outcomes listed in this definition.

If the subject notes any of these symptoms, he/she is instructed to contact his/her physician, who will determine the course of action. PI will be responsible for identifying adverse events during the procedure and during the standard of care follow-up period. Site PIs will review adverse events experienced by subjects treated at their site during the procedure standard of care follow-up period and will record them in the medical record. The study team will review the participant's medical record up to 24 hours after the procedure to monitor if adverse events have occurred. The PI will review all adverse events, expected or unexpected, per standard medical care. PI will classify AEs as expected or unexpected, and report AEs directly to the IRB per WU IRB reporting policy.

Unanticipated problems and noncompliance events will be reported to the WU IRB according to IRB definition and reporting timeframes. Study participants will be followed for 24 hours post-procedure for AEs.

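### The significant hemoptysis definition leaves out bleeding first noted after the procedure, and the AE section contradicts itself on whether events during the procedure count

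*Combined protocol and SAP*

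**What the plan says.** The only secondary outcome is the adverse event rates and safety profile of EBUS-MFB. The rules that decide what is counted stand in two places.

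- **DATA COLLECTION, item (5) Complications.** "Adverse event rates will be documented" is stated without a time limit. Bleeding gets its own category: "Significant hemoptysis will be defined as bleeding noted at the time of procedure that requires a change in the level of care", with blood transfusion as the alternative severity criterion. Pneumothorax, the other complication singled out there, is documented from imaging after the biopsy. Other events from the risks section are to be monitored and reported.
- **Reportable Events, (1) AEs.** For AEs and SAEs, the word "temporally" "will be defined as occurring within 24 hours post-procedure". The same section then says "PI will be responsible for identifying adverse events during the procedure and during the standard of care follow-up period". It adds "The study team will review the participant's medical record up to 24 hours after the procedure to monitor if adverse events have occurred" and "Study participants will be followed for 24 hours post-procedure for AEs".

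The DATA SAFETY MONITORING PLAN also lists symptoms that patients should look out for after the procedure. One is "Continuous bright red blood in your sputum".

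STATISTICAL ANALYSIS gives adverse events as descriptive percentages and sets no window of its own.

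**The concern.** There are two separate issues, both about when an event has to occur in order to count. The 24-hour end of follow-up is taken as given.

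First, the plan expects that a biopsied node may bleed after the patient leaves the suite. It warns patients of the symptom and reviews records for 24 hours. Yet the one named bleeding category admits only bleeding seen at the procedure. A post-procedure bleed serious enough for admission or transfusion would not appear in it, so the significant hemoptysis rate could be understated.

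Second, the AE definition looks only forward from the end of the procedure, while the sentence on finding AEs covers the procedure itself. Two people applying this section in good faith could count different events. The ambiguity falls on the period when the forceps are in use. Because the section also governs reporting to the IRB, it is not only a question of tabulation.

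**Working it through.** The plan states no expected event rate, threshold or test for safety, so there is no figure to reproduce. The check is to take the kinds of event that the plan foresees and classify each under the three rules as written:

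- Rule A: significant hemoptysis (DATA COLLECTION, item 5).
- Rule B: the literal definition of temporal association (Reportable Events, (1) AEs).
- Rule C: the PI's duty to identify events, together with the 24-hour record review (same section).

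| Event | Rule A | Rule B | Rule C |
|---|---|---|---|
| Bleed during the procedure, leading to admission | counted | not counted, onset precedes the window | identified |
| Bleed during the procedure, controlled locally, no change in care or transfusion | not counted, fails severity | not counted | identified |
| Low oxygen or bronchial spasm during the procedure | not applicable | not counted | identified |
| Bleed first noted in recovery or at home within 24 hours, leading to admission or transfusion | **not counted, fails timing** | AE; SAE if hospitalized | identified |

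**Hemoptysis.** The last row is the gap. The event meets the severity test of Rule A and is excluded only by when it was noticed. One could stretch the timing words to cover the recovery area, but not a bleed that starts at home.

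**AE window.** In the first three rows Rules B and C disagree. Rule B is the definition and Rule C is the instruction to the PI. Nothing in the section says which governs, or that the window opens at the start of the procedure.

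**Scale.** Target enrolment is 20 (SUBJECT ENROLLMENT; STATISTICAL ANALYSIS). If one patient has a delayed bleed that meets the severity test and no other bleed qualifies:

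- as written: 0/20 = 0%;
- with the 24 hours included: 1/20 = 5%.

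The procedure ends without EBUS-MFB when on-site cytology is non-diagnostic and no further enlarged node is available (Bronchoscopy, step 4(b)(i)). If m patients undergo EBUS-MFB and m is below 20, one patient is worth 1/m of a rate calculated on those patients, which is more than 5 percentage points. This shows only the granularity of a small study. The documents give no figure for how often delayed bleeding occurs, so no expected bias can be calculated.

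**The case against.** A reader might infer something stronger: that delayed bleeds vanish from the safety results, that intra-procedural events vanish from the AE and SAE rates, and that the technique therefore looks safer overall. The documents do not support this.

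- A bleed within 24 hours of the procedure falls inside the AE definition, and is an SAE if it leads to hospitalization. The record review is the means of finding it. It is missing from one named category, not from the safety record.
- The PI is told in terms to identify events during the procedure. DATA COLLECTION documents AE rates with no time limit and takes in the events listed under RISKS OF PROCEDURES, which include low blood oxygen, bronchial spasm and bleeding from the biopsied site. Vital signs are monitored throughout. The 24-hour phrase may have been meant only to say when follow-up ends.
- The AE definition sits in the safety monitoring plan, among the rules for reportable events. No sentence says that it controls the rates tabulated for the secondary outcome.
- Safety is reported descriptively, and no stated decision depends on the hemoptysis rate. A step of 5 percentage points is true of any single event among 20 patients and is not evidence of bias.

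All of this stands, and it confines the point. It does not remove the timing restriction in the hemoptysis definition, which nothing elsewhere in the plan relaxes. Nor does it reconcile the AE definition with the sentence on the PI's duty.

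**Conclusion.** The point holds in a narrow form and is minor.

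1. Followed as written, the significant hemoptysis rate omits any bleed first noted after the procedure but within the 24-hour follow-up, even if it needs a change in level of care or a transfusion. Any error is in one direction, since the rate can only be understated. At 20 patients one such event is the difference between 0% and 5%.
2. The AE section contradicts itself on events during the procedure. This is an inconsistency that lets two readers compute different rates, not a demonstrated loss of data. Intra-procedural events are probably collected, but on the literal definition they are not AEs or SAEs.

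The first conclusion rests on reading the timing words in their ordinary sense. The second assumes only that a definition and the instruction for applying it should agree. The effect is on one descriptive safety category and on the clarity of the AE definition. The primary outcome, specimen adequacy for PD-L1 testing, is unaffected.

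**What to change.** - **DATA COLLECTION, item (5).** Count as significant hemoptysis any bleeding noted during the procedure, or within the existing 24 hours after it, that meets the severity test already stated. Leave the severity test unchanged.
- **Reportable Events, (1) AEs.** Reconcile the definition of temporal association with the sentence on the PI's duty, so that the window runs from the start of the procedure through the existing 24 hours afterwards. Use the same window for the hemoptysis definition.
- **Data capture.** Record onset as during or after the procedure. Showing the two as separate rows of the safety table would be useful, but that is a reporting choice.

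The cost is two amended sentences and one onset-time field. The 24-hour record review is already planned, and sample size, procedure and length of follow-up do not change. The downside is that reported event rates may be slightly higher.

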#### DATA SAFETY MONITORING PLAN

All subjects enrolled in the trial will undergo routine standard of care bronchoscopy that is indicated as medically necessary by their physicians. Prior to the bronchoscopic procedure, PI will explain the risks associated with bronchoscopy, and verify that the research only risks have been explained, and that the subject has signed an informed consent form. There are no anticipated risks, outside of the risk for the standard of care procedures for this clinical trial. All subjects are required to read, understand, and sign the informed consent form associated with the research study. Each subject will be informed of post procedure symptoms of which to be aware that may represent adverse reactions to the bronchoscopy. Symptoms that the patient will be informed to look out for include:

- Pain or difficulty with swallowing

- Difficulty breathing
- Vomiting
- Dizziness
- Abdominal or chest pain
- Continuous bright red blood in your sputum
- Fever above 100.0 degrees Fahrenheit

If the subject notes any of these symptoms, he/she is instructed to contact his/her physician, who will determine the course of action. All adverse events (AEs) will be reviewed by the medical monitor within one month of their occurrence and summarized for review. The PI will be responsible for submitting this report to the IRB at his/her institution as required. AEs and other reportable events are defined below.

#### *Reportable Events*

##### *(1) AEs*

AEs will be defined as any untoward or unfavorable medical occurrence in a human subject, including any abnormal sign, symptom, or disease, temporally associated with the subject's participation in the research, whether or not considered related to the subject's participation in the research. Regarding AEs and SAEs, "temporally" will be defined as occurring within 24 hours post-procedure. Serious Adverse Events (SAEs) will be defined as any adverse event temporally associated with the subject's participation in research that meets any of the following criteria:

- \* results in death;
- \* is life-threatening;
- \* requires inpatient hospitalization or prolongation of existing hospitalization;
- \* results in a persistent or significant disability/incapacity;
- \* results in a congenital anomaly/birth defect; or
- \* any other adverse event that, based upon appropriate medical judgment, may jeopardize the subject's health and may require medical or surgical intervention to prevent one of the other outcomes listed in this definition.

If the subject notes any of these symptoms, he/she is instructed to contact his/her physician, who will determine the course of action. PI will be responsible for identifying adverse events during the procedure and during the standard of care follow-up period. Site PIs will review adverse events experienced by subjects treated at their site during the procedure standard of care follow-up period and will record them in the medical record. The study team will review the participant's medical record up to 24 hours after the procedure to monitor if adverse events have occurred. The PI will review all adverse events, expected or unexpected, per standard medical care. PI will classify AEs as expected or unexpected, and report AEs directly to the IRB per WU IRB reporting policy.

Unanticipated problems and noncompliance events will be reported to the WU IRB according to IRB definition and reporting timeframes. Study participants will be followed for 24 hours post-procedure for AEs.

In compliance with the Washington University Institutional Data and Safety Monitoring Plan, the Principal Investigator will provide a Data and Safety Monitoring (DSM) report to the Washington University Quality Assurance and Safety Monitoring Committee (QASMC) semi-annually beginning six months after accrual has opened (if at least five patients have been enrolled) or one year after accrual has opened (if fewer than five patients have been enrolled at the six-month mark).

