- d. 8 core biopsies will be obtained from each targeted lymph node using this technique, with each core biopsy specimen placed in formalin for PD-L1 testing.
6. Management of complications: the major complications of bronchoscopic biopsy include pneumothorax and bleeding:
  - a. Pneumothorax: a post procedure chest x ray will be performed following the bronchoscopy. Should a pneumothorax be present, it will be managed by either observation and follow up chest x-ray or by tube thoracostomy at the discretion of the bronchoscopist.
  - b. Bleeding: intra procedural bleeding will be managed using local tamponade, iced saline lavage or mechanical occlusion at the discretion of the bronchoscopist.

Post-bronchoscopy:

1. *Chest x-ray:* A routine portable chest x-ray will be performed on all patients following bronchoscopy as per standard clinical practice at Barnes-Jewish Hospital/Washington University School of Medicine to assess for pneumothorax.
2. *Recovery:* Patients will be recovered in a dedicated post-procedure area as per standard care at Barnes-Jewish Hospital/Washington University School of Medicine

Laboratory Analysis:

1. Formalin placed specimens will be sent for PD-L1 testing using the assay specific for nivolumab.

RISKS OF PROCEDURES:

The greatest risks from bronchoscopy are related to moderate or deep sedation and the very act of passing a bronchoscope into the airway. To mitigate risks of bronchoscopy all patients will be monitored by a nurse and a respiratory therapist during the procedure. In addition, oxygen saturation (using pulse oximetry) respiratory rate, blood pressure, ECG, and heart rate will be continuously monitored. Patients will not be released until they are fully awake and medically stable.

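### Adverse event follow-up is limited to 24 hours, so later consequences of events that begin in that window may be missed in the serious and intervention counts

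*Combined protocol and SAP*

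**What the plan says.** The safety rules are in Data Safety Monitoring Plan, Reportable Events, item (1) AEs. That item uses 24 hours three times:

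- for when an event counts: "Regarding AEs and SAEs, 'temporally' will be defined as occurring within 24 hours post-procedure";
- for the study team's chart review: "The study team will review the participant's medical record up to 24 hours after the procedure to monitor if adverse events have occurred";
- for the participant: "Study participants will be followed for 24 hours post-procedure for AEs".

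The same item lists the SAE criteria. Several look to what the event leads to: death, an event that "requires inpatient hospitalization or prolongation of existing hospitalization", or one that "results in a persistent or significant disability/incapacity". Others look to danger or potential at the time: a life-threatening event, or "any other adverse event that, based upon appropriate medical judgment, may jeopardize the subject's health and may require medical or surgical intervention".

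The item also makes the investigator responsible for identifying AEs over the standard-of-care follow-up period, without giving its length. The opening part of the Data Safety Monitoring Plan has the medical monitor review every AE within one month of its occurrence.

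Data Collection, item (5) Complications, says of pneumothorax that "the number requiring intervention, such as chest tube placement, will be recorded". Bronchoscopy, item 6a, says of a pneumothorax found on the post-procedure film that "it will be managed by either observation and follow up chest x-ray or by tube thoracostomy at the discretion of the bronchoscopist". Neither sentence gives a time limit.

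**The concern.** The classifications ask for information that the stated data collection need not obtain. Whether an event led to admission, to death or to lasting disability, and whether a pneumothorax came to need a drain, may be known only after the first day. The study's own chart review and follow-up are written to end at 24 hours.

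Adverse event rates and the safety profile of EBUS-MFB are the only secondary outcome. If later consequences are missed, the error runs one way. Information that arrives late can add a criterion to an event already recorded, but failing to collect it can only leave the serious and intervention counts too low.

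**Working it through.** **Step 1. Set the rules side by side.** All are from the combined protocol and SAP.

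| Item | What it depends on | Time limit stated |
|---|---|---|
| AE or SAE definition | when the event occurs | 24 hours |
| Study-team record review | what is in the record | 24 hours |
| Participant follow-up for AEs | – | 24 hours |
| Death, hospitalization, persistent disability | later consequence | none |
| Life-threatening, significant disability, may jeopardize health | can be judged early | none |
| Pneumothorax needing intervention | later consequence | none |
| Observation of a pneumothorax with repeat film | – | none |
| Investigator's identification of AEs | standard-of-care follow-up period | length undefined |
| Medical monitor review | events already recorded | within one month |

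**Step 2. Trace one case.** Suppose a pneumothorax is seen on the post-procedure film, is observed, and is drained at 30 hours with an admission (a hypothetical timing). Its onset is in the window, so it is an AE. The admission makes it an SAE by definition, and the drain puts it in the intervention count. Both facts enter the record 30 − 24 = 6 hours after the stated record review ends. No section tells anyone to return to that record or to update the classification.

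**Step 3. Size for one event.** The documents give no safety rate, threshold or precision target, so there is no figure of the plan's own to reproduce. The only numerical input is the target enrollment of 20 (Statistical Analysis). Exact (Clopper-Pearson) 95% intervals:

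- 0/20: upper limit 1 − 0.025^(1/20) = 16.8%, so 0% (0 to 16.8%).
- 1/20 = 5%: lower limit 1 − 0.975^(1/20) = 0.1%; upper limit is the 97.5% point of Beta(2, 19) = 24.9%.
- 2/20 = 10% (1.2 to 31.7%).

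Each missed event moves the rate by 1/20 = 5 points. Patients without a ROSE diagnosis of nonsmall cell lung cancer do not undergo EBUS-MFB, so the denominator for its safety may be below 20. The documents do not give that number. If it were 15 (assumed), one event would be 6.7% (0.2 to 31.9%). If it were 10 (assumed), it would be 10% (0.3 to 44.5%).

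**Step 4. Frequency.** The documents say only that the bronchoscopy risks are extremely low, so the frequency cannot be derived. For illustration, let p be the assumed share of patients with an in-window event that first meets a serious or intervention criterion after 24 hours. The chance of at least one such patient in 20 is 1 − (1 − p)^20:

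- p = 0.1%: about 2%
- p = 1%: 18%
- p = 2%: 33%
- p = 5%: 64%

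None of these values of p comes from the documents, and the conclusion does not rest on them.

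**The case against.** The strongest reply is that the text does not say what a quick reader may take from it.

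- A reader might infer that seriousness is scored and fixed at 24 hours, so that a late-worsening event is scored non-serious. The documents do not support that. The 24 hours in the definition limit when the event occurs, not when its consequence arises, and the chart review is described as a means of detecting events. An in-window event that later leads to admission or death is still an SAE. The gap is one of ascertainment, not definition. This part of the reply stands.
- A reader might also infer that all follow-up ends at 24 hours. The investigator's duty over standard-of-care follow-up and the medical monitor's review are both routes by which a later drain or admission could be seen. That is correct, but neither secures it. The first has no stated length and concerns identifying events. The second sets a latest date for review, so it could take place on day 2. Neither calls for an earlier event to be updated.
- Some criteria can be applied early: life-threatening, the significant limb of the disability criterion, and the judgment-based criterion. True, and an observed pneumothorax might qualify under the last of these. They do not replace the consequence-based criteria or the intervention count.
- The outcome is secondary and descriptive, no stated decision depends on it, and the two intervals in Step 3 overlap widely. This limits the importance of the point but does not remove it.

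**Conclusion.** The point holds as a gap in ascertainment. As written, the follow-up rule can be obeyed in full while a later admission, drain or lasting disability from an in-window event goes unrecorded, and the periods named in the same plan are not reconciled.

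Any resulting error lowers the serious and intervention counts. The documents do not show that the reported rates will be biased downward, only that they could be.

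The size is 5 points per missed event if all 20 patients are in the denominator. In practice that is the difference between reporting no serious event and reporting one. The expected number of missed events is unknown. The PD-L1 adequacy outcome is not affected. The change is worth making because it is cheap and the possible error runs in one direction.

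**What to change.** Leave the 24-hour window for the onset of AEs as it is. In Reportable Events, item (1), reconcile the follow-up periods with a rule along these lines: each AE with onset during the procedure or in the following 24 hours is followed in the medical record until it is resolved or stable, up to a cut-off chosen by the sponsor. The end of the standard-of-care follow-up period (once defined) or the one-month medical monitor review would be natural candidates. State there, and in Data Collection item (5), that seriousness and need for intervention are classified by the worst consequence recorded by that cut-off.

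The cost is a short protocol amendment and a later chart check, needed only for the few patients who have an AE. The serious and intervention rates may look slightly less favourable. No rule of clinical management changes.
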